Community health workers in twelve clinics will identify at least 588 symptomatic contacts (*i.e.* possible TB patients) among 1764 household and close contacts in approximately 2304 eligible index patient clusters over a 16-month period, or up to 7 contacts needing evaluation for TB per referring clinic during each two-month block. With this sample size, assuming a clinic intra-cluster correlation coefficient (ICC) of 0.043 and within-index- patient-cluster ICC of 0.7, and accounting for covariates, we will have 83% power to detect a 15% or greater increase in the proportion completing evaluation from 20% to 35%, at alpha of 0.05, following crossover to the intervention. These estimates account for the proposed stepped-wedge design with 6 steps and a one-step transition period (*i.e.*, an “incomplete” design) at each site. Sample size estimates were reached using PASS 15 and Stata 14, with an extension to account for multiple levels of clustering as per Hemming et al. because index patients and contacts are participants in routine services, and the design of a stepped wedge trial has a fixed duration, we will not limit enrollment if it exceeds these numbers, which may be up to four-fold higher in some or all sites, or more if the intervention strategy is highly effective. For example, if up to 1932 symptomatic contacts, or 23 contacts needing evaluation for TB per referring clinic are identified during each two-month block, we would have 91% power to detect a 10% or greater proportion increase in the proportion completing evaluation from 20% to 30%, at alpha of 0.05, assuming the above noted ICCs.

Evaluation of the fidelity of the intervention strategy

We will propose parallel convergent mixed-methods studies involving quantitative assessments of the fidelity of the implementation strategy and its behavioral mechanisms, using validated psychosocial scales, and we will assess other aspects of fidelity, adaptation, and context through qualitative studies involving interviews and focus group discussions with cases, contacts, community health workers, and community health riders.

However, prior to that, we describe our plans in this protocol to validate quantitative study instruments.

Quantitative studies

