Statistical Analysis Plan: HCD-CoP Study

NCT05640648

Trial Title	A User-Centered Strategy to Improve Delivery of TB Contact Investigation in Uganda: A Stepped-Wedge Cluster Randomized Implementation Trial
Grant Title	Human-centered Design and Communities of Practice to Improve Delivery of Home-based TB Contact Investigation in Uganda
Grant Acronym	HCD-CoP
Trial Registration	ClinicalTrials.org
Principal Investigators	[name], [name]
Date	May 2, 2023

I. Introduction

1. Study Aims

Primary Objective

Aim 1: To compare the implementation, effectiveness, and public health impact of a user-centered strategy versus the standard strategy for implementation of TB contact investigation in a stepped-wedge, cluster-randomized implementation trial.

- **User-centered Strategy:** Training + Supportive Supervision + Electronic Data Collection + Facilitation Tools + Communities of Practice
- **Standard Strategy:** Training + Supportive Supervision + Electronic Data Collection

Secondary Objectives

Aim 2: To identify processes and contextual factors that influence the implementation, effectiveness, and public health impact of the user-centered contact investigation strategy.

Aim 3: To compare the costs and epidemiological impact of the user-centered and standard implementation strategies for TB contact investigation.

Overview

This statistical analysis plan covers the primary objectives of assessing the implementation and key secondary effectiveness and public health impact outcomes. **This document will not further address the trial's secondary objectives of assessing implementation fidelity and context (Aim 2) and implementation costs and impact at scale (Aim 3).** Study endpoints will be evaluated through a review of data entered into the HCD-CoP CommCare (Dimagi, Boston, MA) database by community health workers as part of their routine TB contact investigation activities, with validation of effectiveness endpoints using source data entered into Uganda National TB and Leprosy Programme TB treatment registers for all patients initiating TB treatment at participating health facilities. Trial results reporting will follow the CONSORT 2010 statement extension for stepped-wedge trials (**SWT**).^[1, 2] This statistical analysis plan is written in support of and is entirely consistent with the full trial protocol; however, in case of any discrepancies, this statistical analysis plan takes precedence.

1. Trial Summary

Trial Design

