The study proposes to conduct a stepped-wedge, cluster-randomized implementation trial of a novel, user-centered implementation strategy for the delivery of TB contact investigation at 12 TB diagnostic and treatment units (DTUs) located at health facilities in central Uganda. The trial over will proceed over the course of 16 trial steps, each 8 weeks in duration, with the intervention period lasting from as little as 16 weeks up to 56 weeks at the participating facilities. We will use a complete stepped-wedge design, including an 8-week transition period for training and initial adoption, followed by 8 to 52 weeks of post-intervention data collection at each site. Data collected during the transition periods will not be included in the final analysis. In addition, the trial will be paused for 6 weeks during the annual 2022-2023 year-end holiday period (12 December 2022 through 15 January 2023; all transition periods falling during and after this pause period will be delayed by six weeks and patients recruited during this period, as well as the data of their contacts, will be excluded from the trial.[§] The rationale for this pause is that staffing levels and patient visits are low during this period, and without exclusion, this could bias the trial results in uncertain ways.

§Version 2.0 Update: On 15 October 2022, the President of Uganda announced Ebola-related public health restrictions preventing public movement in two districts where two study sites are located: Mubende and Kasambya. As a result, the principal investigators immediately paused all new introductions of the study intervention effective immediately for the subsequent 8-week period ending 11 December 2022, effectively extending the previously proposed 6-week study pause by at least 14 weeks. The original schema is shown below in Figure 1, and an updated schema is shown below in Figure 2.

[figure not shown]

Figure 1. HCD-CoP Intervention Randomization and Enrolment Schedule.

Legend: Ordinal numbers indicate the cross-over sequence from standard to the intervention period. Note that pause periods are not shown in the current figure.

Group	Site	Month																	
		1 Mar 7 - Apr 3	2 Apr 4 - May 1	3 May 2 - May 29	4 May 30 - Jun 26	5 Jun 27 - Jul 24	6 Jul 25 - Aug 21	7 Aug 22 - Sep 18	8 Sep 19 - Oct 16	9 Oct 17 - Nov 13	10 Nov 14 - Dec 11	Holiday	11 Dec 12 - Jan 15	12 Jan 16 - Feb 12	13 Feb 13 - Mar 12	14 Mar 13 - Apr 9	15 Apr 10 - May 7	16 May 8 - Jun 4	17 Jun 5 - Jul 2

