To inform our sample size calculations, we used a conservative estimate of the average number of index TB patients of 11 per clinic per 8-week block period (g), assuming a rho-alpha of 0.172 and rho-beta of 0.647 from our preliminary data, and an average number of symptomatic contacts per index TB case (m) of 1, as well as a pre-intervention proportion of patients completing treatment (p1) of 0.4, a post-intervention proportion of treatment completion (p2) of 0.6, the number of clusters crossing at each step (k) of 2, and total steps (steps) of 6.

Using the Stata command:

steppedwedgeTwoLevelsD, binomial complete(1) vartotal(1) p1(0.4) p2(0.6) m(1) k(2) rho(0.172) rho2(0.647) alpha(0.05) steps(6) g(11),

We estimate that the trial will conservatively need 924 total symptomatic contacts of index TB patients to achieve a power of 99%. Sample size estimates were reached using PASS 15 and Stata 16, with an extension to account for multiple levels of clustering as per Hemming et al.[3] and Davis-Plourde [4]. Although some sample size estimators predict 100% power, 100% power is not theoretically achievable, and therefore rendered as 99%. Because index patients and contacts are participants in routine services, we will not limit enrollment if it exceeds these numbers, which we project may be higher by four-fold or greater if the intervention strategy is highly effective.

Tests for Two Proportions in a Stepped-Wedge Cluster-Randomized Design

Design type: Complete

Test statistic: Wald Z-Test

$H_0: P_1 - P_2 = 0$.

$H_A: P_1 - P_2 = D_1 \neq 0$.

ICC (intra-cluster correlation coefficient (rho)) measures the correlation of observations within a group/cluster. It indicates the dependency of observations on the group/cluster they belong to. Mathematically, it is calculated as the variance between groups/clusters divided by the total variance (which is variance between groups plus variance within groups). Thus, the higher the correlation within the groups (meaning less variability within groups/clusters), the lower the variance within groups leading to a higher ICC. The converse is also true, in that the lower the correlation within groups (meaning less variability within groups/clusters), the higher the variance within groups leading to a lower ICC.

Table 2: Power and sample size (total number of symptomatic contacts of index TB patients) estimation

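### The protocol's 83% and 91% power cannot be reproduced for the incomplete design it describes, and SAP Table 2 computes power for a complete design although transition data are excluded

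*Protocol*

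**What the plan says.** **Protocol, Section I item 4, Sample Size.** With 588 symptomatic contacts (7 per clinic per two-month block), a clinic ICC of 0.043 and a within-index-patient ICC of 0.7, "we will have 83% power to detect a 15% or greater increase in the proportion completing evaluation from 20% to 35" per cent. With 1932 contacts (23 per block), "we would have 91% power to detect a 10% or greater proportion increase in the proportion completing evaluation from 20% to 30" per cent. On the design: "These estimates account for the proposed stepped-wedge design with 6 steps and a one-step transition period", which the same sentence calls incomplete. The 83% is also described as "and accounting for covariates", with no size given for the gain. The section does not state the sidedness of the test, the variance convention, the number of periods, or the number of symptomatic contacts per index patient used in the calculation.

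**SAP, Overview.** "in case of any discrepancies, this statistical analysis plan takes precedence".

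**SAP, Trial Design.** "We will use a complete stepped-wedge design, including an 8-week transition period for training and initial adoption". Shortly after: "Data collected during the transition periods will not be included in the final analysis". The dataset assembly paragraph under Statistical Methods repeats the exclusion.

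**SAP, Power and sample size calculation.** The Stata command sets the `complete(1)` option, and the test description reads "Design type: Complete". The definitions under Table 2 set the number of periods to the number of steps plus one, which leaves no block for a transition. The Summary cites 99.8% power for the 8-cluster contingency, which it calls the worst case.

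**The concern.** A transition block that is left out of the analysis removes, for each clinic, the observations next to its crossover. In a stepped-wedge design with period effects these carry much of the information about the intervention. A power figure for a complete design therefore overstates the power of the same design with the transition removed, even if the number of analysed contacts is unchanged.

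The totals cannot show which design was used. 588 = 12 × 7 × 7 and 1932 = 12 × 7 × 23 fit a complete seven-period design, and they also fit an eight-block design with one block per clinic removed. The printed powers have to be checked directly.

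At stake is whether the stated power belongs to the design that will be analysed. This matters most for the SAP's contingency rows, where fewer clusters leave less margin.

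**Working it through.** **Model.** Clinic-period means, fixed period effects (as in the protocol's Statistical Considerations), a random clinic intercept, and a two-sided Wald test at 0.05. With v = p1(1−p1) and n contacts per clinic-block, the clinic variance is τ² = ICC × v and the error variance of a cell mean is σ² = (1−ICC) × v / n. One symptomatic contact per index patient is assumed, so the 0.7 ICC drops out. Power = Φ(δ/SE − 1.960).

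For a complete design with I clusters and T periods,

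Var = I σ²(σ² + Tτ²) / [(IU − W)σ² + (U² + ITU − TW − IV)τ²],

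where U is the number of treated cells, W the sum of squared column totals and V the sum of squared row totals.

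**Protocol figures, complete design.** I = 12, T = 7, two clinics per step: U = 42, W = 364, V = 182. So IU − W = 140 and U² + ITU − TW − IV = 560. With v = 0.16, τ² = 0.043 × 0.16 = 0.00688.

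- 20% to 35%, n = 7: σ² = 0.957 × 0.16 / 7 = 0.02187. Var = 0.018383 / 6.9152 = 0.002658, SE = 0.05156. Power = Φ(0.15/0.05156 − 1.960) = 82.9%. Printed: 83%.
- 20% to 30%, n = 23: σ² = 0.957 × 0.16 / 23 = 0.00666. Var = 0.0043793 / 4.7848 = 0.000915, SE = 0.03025. Power = Φ(0.10/0.03025 − 1.960) = 91.1%. Printed: 91%.

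**Same inputs, transition block removed.** The generalised least squares information is summed over the observed cells only.

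| Design | SE, 20% to 35% | Power | SE, 20% to 30% | Power |
|---|---|---|---|---|
| Complete, 7 periods | 0.05156 | 82.9% | 0.03025 | 91.1% |
| Transition removed, 8 blocks (7 observed) | 0.06165 | 68.2% | 0.03607 | 79.2% |
| Transition removed, 7 blocks (6 observed) | 0.06303 | 66.3% | 0.03768 | 75.6% |

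Eight blocks match the protocol's 16 months and keep the totals at 588 and 1932. Averaging the variance over p1 and p2 instead lowers the eight-block figures to about 60% and 73%.

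**Covariate gain needed.** If covariates cut the variance by 30%, the eight-block SEs are multiplied by √0.70 = 0.837, and the powers become 82.9% and 91.2%. Reductions from about 29% to 31% round to both printed figures.

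**SAP Table 2, reproduced.** A complete design with clinic variance 0.172v and cell error (1 − 0.647)v/11 matches all 12 printed powers to four decimals. For example, 8 clusters and 5 periods, 20% to 40%: U = 20, W = 120, V = 60; τ² = 0.02752; σ² = 0.353 × 0.16 / 11 = 0.005135. Var = 0.0058635 / 3.5078 = 0.0016716, SE = 0.04088. Power = Φ(0.20/0.04088 − 1.960) = 0.9983, as printed.

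**SAP Table 2, only the transition removed.** One block is added, so each cluster still has the same number of observed blocks and N is unchanged.

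| Clusters | Proportions | Complete (as printed) | Transition removed |
|---|---|---|---|
| 12 | 20% to 40% | 1.0000 | 1.0000 |
| 10 | 20% to 40% | 1.0000 | 0.9985 |
| 8 | 20% to 40% | 0.9983 | 0.9585 |
| 8 | 25% to 45% | 0.9948 | 0.9267 |

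For the 8-cluster rows the SE rises from 0.04088 to 0.05415 (20% to 40%) and from 0.04426 to 0.05862 (25% to 45%).

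**The case against.** **The covariate gain is a stated input of unknown size.** The 68.2% and 79.2% set it to zero. This stands. Nor does matching two scenarios settle the matter. Removing the transition inflates the SE by nearly the same factor in both (0.06165/0.05156 = 1.196 and 0.03607/0.03025 = 1.192), so one gain of about 30% restores both. A reader might infer that the transition was simply forgotten and that the true power is 68% and 79%. The documents do not support that; they show only that the figure cannot be checked, and that it matches a design without a transition if no gain was used.

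**Table 2 does not fully back the conventions.** It agrees on the two-sided alternative, on p1(1−p1) and on one contact per index patient. It differs on the second ICC: matching Table 2 requires the second ICC to shrink the error variance even with one contact per index patient. Carried to the protocol (error 0.3v/n), that handling gives 99.8% and 99.99% for a complete design, neither of which is printed. The support is therefore partial.

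**The consequence is small.** The SAP governs, uses other inputs, and does not cap enrolment. At its planning value of 11 per clinic-block, the transition-removed protocol model gives 84.4% for 20% to 35% (clinic ICC 0.043). The SAP also reports 22.7 index patients per clinic in the pre-trial block. This stands, and it sets the priority. It does not remove the SAP's own mismatch between the design analysed and the design powered.

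**Complete might only mean that data are collected throughout.** Power depends on the data analysed, and the SAP excludes the transition data.

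**Conclusion.** The point holds, at low priority. The protocol's 83% and 91% cannot be reproduced for the incomplete design from what is reported. Under three unstated conventions they match a complete seven-period design to about 0.1 percentage point, and the same conventions with the transition removed give 68.2% and 79.2% (eight blocks) or 66.3% and 75.6% (seven). This rests on those conventions and on no covariate gain.

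The SAP part is firmer, because the text alone shows transition data excluded and power computed as complete. Its size rests on the calculation that matches every Table 2 entry: no visible change with 12 clusters for 20% to 40%, 0.9985 with 10, and 0.9585 rather than 0.9983 with 8.

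Three stronger readings should be resisted:

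- That the trial is underpowered. The 12-cluster SAP case stays at 1.0000 when only the transition is removed.
- That the transition alone takes the SAP case (20% to 40%) to 98.1%, 90.2% and 68.5% for 12, 10 and 8 clusters. Those values also raise the error variance share from 0.353 to 0.828, which is a separate question about how the second ICC enters.
- That clustering of several symptomatic contacts per index patient lowers the protocol figures further. 588 symptomatic contacts from about 2304 index patients is 588/2304 = 0.26 per index patient, so the documents give no basis for assuming two or more.

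**What to change.** - Re-run SAP Table 2 with the transition cells removed, including the 10- and 8-cluster rows, and restate the powers. The 99.8% worst-case figure in the Summary should change with them.
- Correct the complete label in the SAP's Trial Design and power sections, so that it agrees with the exclusion of transition data.
- Re-run the protocol's calculation the same way and restate the 83% and 91%. If a covariate gain was used, give its size and justification.
- For both calculations, state the design matrix, the variance convention, the number of symptomatic contacts per index patient and any covariate gain. In the SAP, also state how the second ICC enters when there is one contact per index patient.

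The cost is one re-run of each calculation, a wording change, and possibly less favourable stated figures for the protocol and the 8-cluster contingency. No extra enrolment is needed.

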We will compare the two strategies overall (1°) and for each stage of the contact investigation cascade (2°), as well as yield of diagnoses/treatments for active and latent TB (2°). We will construct multilevel logistic models (or Poisson models for counts), adjusted for clustering within clinics/communities and within index patient clusters, to estimate proportions (or counts) with exact binomial 95% confidence intervals. We will compare primary outcomes between control and intervention periods using adjusted chi-squared tests of proportion. We will determine and report ICC at both health centre and index patient levels. We will fit a multilevel, generalized linear mixed-effects model with a logit link and random effects for clustering and fixed effects for step (*i.e.*, point in time). For sustainability we will analyze the interaction between intervention and time-elapsed-since-intervention-initiation to determine if the intervention effect strengthens or weakens over time as it becomes routinized, looking at both TB evaluation and diagnosis. We will also explore variation in delivery processes and outcomes for the following:

- (1) Health facility clusters,
- (2) Community health workers, and
- (3) Clinically important sub-groups including women, men, younger children (age<5), older children (age 5-14), adults, and PLHIV, all in pre-specified sub-group analyses.

There is a strong biological rationale for each of these analyses, given known differences in TB diagnostic performance by sex and in WHO recommendations for TB evaluation by age and HIV status.

We will prepare flow and cascade diagrams to illustrate key contact investigation process measures, as in our previously published work. We will produce time-series graphs demonstrating change in cumulative likelihood of completion of contact investigation and each of the component process measures over time. We will prepare tables describing associations between provider and clinic characteristics and likelihood of completion, stratified by key individual- and household-level characteristics of community members. Tests of significance will be applied as needed at the adjusted $p<0.05$ level.

Primary Outcomes

1. Referred contacts completing TB evaluation
 - a) Count (Number of contacts who complete TB evaluation within 60 days of index patient diagnosis)

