- a) *Outcome definition:* Number of contacts who complete TB evaluation within 60 days (ctevalcomplete60) of index patient treatment initiation divided by the total number of contacts screening TB symptom positive (ctevaleligible). This will be an aggregate, cluster-level, exposure-specific (control versus intervention) measurement.
- b) *Outcome analysis:* Difference in log odds of the outcome between the intervention and control exposure periods using the Logit model (*n.b.*, this will be the same for all proportional outcomes)

Secondary Outcomes

- a. **Effectiveness** (*i.e.*, clinical effectiveness)
 - i. Proportion of contacts diagnosed with active TB (also known as the active TB treatment yield of TB contact investigation, or the number needed to screen):
 - a) *Outcome definition:* Number of contacts diagnosed with active TB (definitions below) and initiated on treatment within 60 days of index patient treatment initiation divided by the total number of contacts encountered.
 - (i) Microbiologically confirmed active TB: Diagnosed by a positive AFB-smear microscopy result, GeneXpert result, or other accepted *Mtb*-specific microbiologic test (*e.g.*, urinary LAM or mycobacterial culture)
 - (ii) Clinically confirmed active TB: Active TB diagnosed clinically, based on clinically diagnosed extra-pulmonary TB or a decision to initiate presumptively for active pulmonary TB.
 - b) *Outcome analysis:* As above
 - ii. Proportion of contacts initiating TB preventative therapy (TB preventative therapy yield of TB contact investigation):
 - a) *Outcome definition:* Number of TB contacts initiated on TB preventive therapy within 60 days of index patient treatment initiation divided by the total number of contacts eligible for TB preventive therapy
 - (i) Children under age 5
 - (ii) Persons living with HIV
 - (iii) Older adolescent (age ≥ 15 years and adult household and other close contacts with a positive TST and in whom active TB has been excluded by symptoms and/or testing)
 - b) *Outcome analysis:* As above
- b. **Public Health Impact** (*i.e.*, public health effectiveness)
 - i. Count of contacts diagnosed with active TB:
 - a) *Outcome definition:* Number of contacts diagnosed with active TB (definitions below) and initiated on treatment within 60 days of index patient treatment initiation
 - (i) Microbiologically confirmed, as defined above
 - (ii) Clinically confirmed, as defined above

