Merged datasets will be extracted from CommCare, transferred to Stata, and re-arranged into working analytic files and checked for completeness. We will generate time-slice and exposure variables including the control-intervention exposure defining variable (var), the cluster-month var, cluster-exposure var, exposure-month var, and the exposure-time-cluster variable. The transition period will be excluded from the analysis as indicated in the trial design section 2.1 above.

There are 12 study sites that were assigned into six groups (2 facilities per group) and one group at a time will be switched from the standard pre-intervention to the user-centered implementation strategy during 8-week training and transition intervals in a randomly assigned order. Within each of the 6 groups, cluster-level covariates (outcomes, predictors, and confounders) will be formed by aggregating individual-level participants' data. For every cluster, each outcome (primary, secondary, and implementation) occurring

during the study period will be assigned to that cluster, the exposure condition (pre-intervention or intervention), and the trial month in which it occurred. A group-specific summary measure of the outcome, Y_{ij} (for i exposure and j period) will be calculated as a mean (SD) for continuous and count variables, and mean proportion for binary variables. From the Y_{ij} s, we will then calculate the cluster-period summaries $\Sigma Y_{ij} / n$, where n =number of months in i exposure, and estimate unadjusted period-specific intervention effect (θ) based on these cluster-period summaries.

b. Baseline assessment and trend analysis

Baseline measures of all outcomes will be calculated using data collected in the pre-intervention period months 1 and 2 (Figure 1).

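### Exact binomial intervals do not fit multilevel estimates or counts, the chi-squared test does not state its adjustment, and one SAP summary averages calendar month away

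*Protocol*

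**What the plan says.** Three passages matter.

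- **Intervals.** Protocol section 13 (Statistical Considerations) plans multilevel logistic models, or Poisson models for counts, "adjusted for clustering within clinics/communities and within index patient clusters", and uses them "to estimate proportions (or counts) with exact binomial 95% confidence intervals".
- **Test.** The next sentence reads: "We will compare primary outcomes between control and intervention periods using adjusted chi-squared tests of proportion". It does not say what the adjustment is for. The paragraph then specifies a multilevel "generalized linear mixed-effects model with a logit link and random effects for clustering and fixed effects for step".
- **Cluster summaries.** SAP, Statistical Methods a (Dataset assembly), defines a summary Y_ij for exposure i and period j, sums it, and divides by n, the number of months in exposure i. From these values it will calculate the intervention effect: "and estimate unadjusted period-specific intervention effect".

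The SAP mentions neither exact binomial intervals nor a chi-squared test, and gives no method for confidence intervals. Its Overview describes it as consistent with the Protocol and gives it precedence where the two differ.

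**The concern.** A Clopper-Pearson interval is a function of the number of events and the number of observations only. It cannot carry the clinic and index-patient correlation that the same sentence says the model adjusts for. For a count it has no denominator, and the Protocol's first primary outcome is partly a count. Readers of the trial report will look first at the proportion completing evaluation in each phase, and its error bars would understate the uncertainty.

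The other two items concern time. In a stepped wedge, control data come earlier than intervention data by design. A control-versus-intervention comparison with no time term therefore counts any secular change as intervention effect. The SAP itself expects disturbance of this kind from the Ebola restrictions.

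**Working it through.** **Inputs.** Protocol section 4, Sample Size: "Community health workers in twelve clinics will identify at least 588 symptomatic contacts", "assuming a clinic intra-cluster correlation coefficient (ICC) of 0.043", and up to 7 contacts per clinic per two-month block. SAP, Power and sample size calculation: 924 symptomatic contacts, 11 index patients per clinic per period, one symptomatic contact each, clinic ICC 0.172, 12 clinics, 7 periods.

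**Reproducing the plan's figures.**
- Contacts: 12 x 7 x 7 = 588 and 12 x 11 x 7 = 924.
- Power, using the Hussey-Hughes variance (period fixed effects, clinic random intercept, control-arm variance, 7 complete periods): 0.829 for 20% to 35% with 588 contacts, against the stated 83%; 0.911 for 20% to 30% with 1932, against the stated 91%.
- So the contact numbers and ICC are read as the Protocol used them. With the transition period removed, as the Protocol says was done, power for 588 contacts is 0.66 to 0.68. That is a separate matter and does not enter below.

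**Single-phase proportion.** Half of each clinic's contacts fall in each phase, m per clinic-phase. DEFF = 1 + (m - 1) x ICC; width factor = sqrt(DEFF); actual coverage of a nominal 95% interval = 2 x Phi(1.96 / sqrt(DEFF)) - 1.

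| | Protocol inputs | SAP inputs |
|---|---|---|
| m | 588/24 = 24.5 | 924/24 = 38.5 |
| DEFF | 1 + 23.5 x 0.043 = 2.01 | 1 + 37.5 x 0.172 = 7.45 |
| Width factor | 1.42 | 2.73 |
| Coverage | about 83% | about 53% |

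Examples: 59/294 (20%) has an exact interval of 15.6 to 25.1%, and about 13.5 to 26.5% after widening by 1.42. For 185/462 (40%) it is 35.5 to 44.7%, and about 28 to 52% after widening by 2.73.

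Two sensitivities move the factor in opposite directions.
- *Unequal exposure.* Clinics spend 1 to 6 periods in each phase. This raises the factors to 1.44-1.50 and 2.79-3.00.
- *Decay.* Suppose correlation between periods is half that within a period (an assumption). With 3.5 periods per phase, DEFF = 1 + 6 x 0.043 + 17.5 x 0.0215 = 1.63 (factor 1.28) and 1 + 10 x 0.172 + 27.5 x 0.086 = 5.09 (factor 2.25).

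**Pooled contrast between phases.** Clinic effects partly cancel because every clinic contributes to both phases. In the complete design, a clinic crossing after s periods has net weight (7 - 2s)/42. The squared weights over 12 clinics sum to 140/1764 = 0.0794. With n contacts per clinic-period, the variance ratio to a naive calculation is 1 - ICC + ICC x 0.0794/(2/(42n)).
- n = 7, ICC 0.043: 0.957 + 0.043 x 11.67 = 1.46, factor 1.21.
- n = 11, ICC 0.172: 0.828 + 0.172 x 18.33 = 3.98, factor 2.00.

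Dropping the transition period raises these to as much as 1.25 and 2.15. The 1.4 to 2.7 range therefore does not carry over to contrasts.

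**Calendar time.** Take the Protocol's 16-month trial with crossovers from month 3 and two-month transitions. Group g is in control for months 1 to 2g (mean g + 0.5) and in intervention for months 2g + 3 to 16 (mean g + 9.5). The gap is 9 months in every site. Pooled over site-months, the means are 203/42 = 4.8 and 511/42 = 12.2, a gap of 7.3 months. An *assumed* trend of 1 point per month would add about 7 points (pooled) or 9 points (within site) to a contrast not adjusted for time, against the SAP's 20-point target difference. The documents give no trend estimate, and the schedule lengthened by the Ebola pause would change the gaps.

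**If the chi-squared test adjusted for nothing.** Simulated rejection rates with no intervention effect (complete 7-period design, 4000 runs) are about 11% (ICC 0.043) and 33% (ICC 0.172) with no trend. With an assumed rise of 2 points per two-month period they are about 34% and 51%.

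**The SAP summary.** Y_ij carries a period index j. Summing over j and dividing by the months in the exposure leaves one value per cluster and exposure. No period remains, so no period-specific effect can be formed from it. SAP Statistical Methods b needs the month kept, because it compares groups in different exposures during the same trial month.

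**The case against.** The strongest reply is that none of this touches the main inference, and that reply largely stands. Protocol section 13 has random effects for clustering and fixed effects for step. SAP Statistical Methods c adjusts for clinic as a random effect, and Equations 3 and 4 contain step terms. The SAP is the later document, takes precedence, and draws its effect estimates from fitted mixed models. It already assigns outcomes to trial months and plans same-month comparisons.

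A reader might infer more than the documents support, in four ways.

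- *That the trial ignores clinic clustering.* It does not. The models adjust for it, the chi-squared test is called adjusted, and the SAP summaries are cluster-level. Their fault is the loss of time.
- *That the reported effects absorb any trend.* This fits only a contrast without a time term. Some SAP time provisions are conditional (adjustment for trial period as appropriate; segmented regression if trends are found), but the main equations include step.
- *That the primary outcome is analysed as a phase aggregate*, because it is described thus: "This will be an aggregate, cluster-level, exposure-specific (control versus intervention) measurement". That line defines the outcome; the line after it assigns a logit model.
- *That 1.4 to 2.7 applies to the treatment comparison.* For the pooled contrast the factor is about 1.2 to 2.1.

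Precedence does not settle the interval question. The SAP is silent on intervals for the displayed phase proportions and counts, so it offers nothing to replace the Protocol's method.

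**Conclusion.** The point holds in limited form. The exact binomial interval is wrong as written for clustered proportions and undefined for counts. Computed on pooled phase counts, it would be about 1.4 to 2.7 times too narrow for a single-phase proportion. This assumes equal phase halves, constant clinic-period size and the clinic ICC alone; with about one symptomatic contact per index patient, the index-patient ICC adds little. The 2.7 also assumes that an ICC from about two months of pre-trial data applies undiminished across a phase.

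The chi-squared test is ambiguous rather than shown to be wrong: its adjustment is unstated and no time term is given. The SAP's month-averaged formula contradicts both the effect that it names and the same-month comparisons planned in the following section. The 7 to 9 points of trend bias are an illustration under an assumed trend. The main mixed-model analysis is unaffected.

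**What to change.** 1. In Protocol section 13, delete the exact binomial intervals. State in the SAP that phase proportions and counts, with their 95% intervals, are marginal predictions from the period-adjusted mixed model, or use cluster-robust intervals.
2. Drop the chi-squared test in favour of the mixed-model test of the intervention term.
3. In SAP Statistical Methods a, keep completers and denominators by clinic and month. Form any unadjusted contrast between clinics in different exposures within the same month, then average over months, in line with section b. Label it descriptive.

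The cost is wording in both documents, with no new data. Reported intervals will be wider.
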